## **Laboratory Assessments**

7. **Safety laboratories**: Safety labs will be measured at the screening visit. These will include a complete blood count and a comprehensive metabolic panel.
8. **Biomarker**: Most biomarkers will be collected at baseline and after each treatment arm to determine if the treatment results in a change in these biomarkers. Baseline biomarkers will help understand whether treatment response can be predicted from biomarker tests.
  - a. Buccal swabs will be collected to assess mitochondrial function.
  - b. Plasma, Peripheral Blood Mononuclear Cells (PBMCs), DNA, and RNA will be collected and stored locally for future analysis, such as oxidative and methylation metabolism, bioenergetics, immune biomarkers, gene expression, epigenetics, and gene sequencing. 3billion Laboratory in Seoul, South Korea will perform genetic sequencing to look for causative mutations if good quality DNA is obtained and can be isolated. Samples will be stored until they are used up or destroyed, when possible. The PI, [name], will retain control over the blood sample unless it is requested that the sample be destroyed and then it will not be used for any future studies. If the participant wishes to have the sample removed from storage and destroyed at any time, they may contact a study coordinator or PI. IRB permission will be obtained prior to sharing samples for future studies. These samples will be de-identified and no protected health information will be shared with collaborators. If samples are shared, a log of those who withdraw samples will be documented thoroughly.
  - c. Deciduous teeth and hair samples will also be collected and sent to [name] laboratory. Recent research suggests prenatal nutritional metal concentrations measured in deciduous teeth correlate with long-term language development and may predict treatment response and other recent studies support the measurement of unique metabolic markers using hair samples.
  - d. Folate receptor  $\alpha$  autoantibody (FRAA) titers will be sent to the laboratory of [name], Ph.D. at the State University of New York, Downstate (Brooklyn, NY) or Iliad Neurosciences. We have demonstrated in one study that FRAA are related to methyl-B12 metabolism.
  - e. Saliva will be collected from the participant and biological parents to investigate whether single nucleotide polymorphism (SNPs). Parental SNPs are important to understanding whether the SNPs in the children are significant or not – for example, if parents have the same SNP profile as the child, the SNP is unlikely to have a significant effect of pathophysiology.
  - f. Autoantibodies to neuronal tissue may be assessed by the Laboratory of [name] at the University of Oklahoma Health Sciences Center in Oklahoma City, OK if enough sample is available for the assay.

## **Medical Assessments**

9. **Medical and Psych History**: This structured questionnaire form assists with the elicitation and assessment of health complaints, appetite, sleep, activity level and general health at **baseline**. The companion measure, the Adverse Effects Review, is used in follow up visits to monitor and document new events during the trial.

10. **Suicidality Assessment**: Although we do not anticipate any symptoms consistent with suicidality, an assessment of suicidality is required in FDA trials involving psychiatric disorders including ASD and is a standard assessment in FDA regulated ASD trials. An assessment similar to other studies examining ASD children will be used. The Columbia-Suicide Severity Rating Scale (C-SSRS) fulfills this requirement.

## **Developmental Assessments**

11. **Childhood Autism Rating Scale (CARS)**: This 15-item scale can be used to both diagnose autism and ASD, and to assess the overall severity of symptoms.

Full Study Title: Effect of a Wide Spectrum Nutritional Supplement on Mitochondrial Function in Children with Autism Spectrum Disorder (ASD)

Principal Investigator: [name]; Co-Investigators: [name]

Sponsor: [name]; IND 142751; ClinicalTrials.gov ID: NCT03835117; Protocol Version 02/11/2022

Funding Source: Turnabout for Autism (Private Foundation), Pleasanton CA.

12. Differential Abilities Scale (DAS): This scale is a scale that assesses cognitive abilities and early learning and has been validated against other cognitive ability scales (Wechsler, Bayley, etc.). This scale is designed to identify clinical risk and disability.

13. Ohio Autism Clinical Impression Scale (OACIS): A clinical evaluation by the study physician of initial severity of 10 ASD-related symptoms at baseline on a 7-point scale (Part 1), and a clinical evaluation of change of those symptoms using a different 7-point scale (very much improved to very much worse). The 10 items include social interaction, aberrant/abnormal behavior, repetitive/ritualistic behavior, verbal communication, non-verbal communication, hyperactivity/inattention, anxiety/fears, sensory sensitivities, restricted/narrow interests, and autism.

14. Clinical Global Impression - Severity (CGI-S): This is a 7-item scale ranging from a score of 1 for "Normal" to 7 for "Extreme" . All aspects of the child's condition need to be integrated to assign the CGI-S score. Only participants of CGI-S of 4 ("moderate") or greater severity will be included in the trial. By definition, a child with ASD and language impairment (which is established at screening) has moderate severity ASD. Thus, the CGI-S will be completed at baseline since it requires all available information about the child. CGI-S will be rated by an assessor who is blind to treatment assignment. Both the standard CGI-S and the newly developed CGI-S-ASD will be completed, with the CGI-S completed before the CGI-S-ASD.

15. Clinical Global Impression for Improvement (CGI-I): The CGI-I is a 7-point measure of overall symptomatic change compared to baseline  that will be used as a **key primary** outcome measure. Scores range from 1 (Very Much Improved) through 4 (Unchanged) to 7 (Very Much Worse). All aspects of the child's condition need to be integrated to assign the CGI-I score. The CGI-I will be rated by an assessor who is blind to treatment assignment, AEs, and medication dose. Both the standard CGI-I and the newly developed CGI-I-ASD will be completed, with the CGI-I completed before the CGI-I-ASD. Ratings of Much Improved or Very Much Improved on the CGI-I will be used to define positive response.

16. Parent Target Problems (PTP): At baseline, parents will be asked to nominate the two most important ASD problems for the child. Through brief discussion, the frequency (for episodic behaviors such as insists on daily routines) or constancy (for problems such as language delay or rigidity reflecting more enduring patterns), intensity and impact of the behavior on the family are established. Responses from this systematic inquiry are documented in a brief narrative. The narrative will be reviewed monthly and a new narrative documented. This review will assist with the scoring of the CGI-I in real time.  At the end of the trial, the narratives will be reviewed by a panel blind to treatment assignment. This method has been shown to be reliable and valid in placebo-controlled studies. 

17. Children's Yale-Brown Obsessive-Compulsive Scales-ASD (CYBOCS-ASD): The CYBOCS-ASD is a modified version of the CYBOCS developed for children with Obsessive-Compulsive Disorder.  The modified version is a semi-structured clinician-rated scale designed to rate the current severity of repetitive behavior in children with ASD (i.e., Time Spent, Interference, Distress, Resistance, and Control). Each item is scored from 0 (least symptomatic) to 4 (most symptomatic), yielding a Total score from 0 to 20. It has established reliability and validity  and is sensitive to change. 

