Investigational Product	Weight adjusted wide-spectrum oral nutritional supplement powder and gel capsules that targets mitochondrial support produced by NeuroNeeds (Old Lyme, CT) taken in two divided doses vs oral placebos.
Safety	Physical examination, safety labs, Adverse Event Reporting, safety monitoring
Statistical Methods	The primary analysis will be intent-to-treat, defined as all randomized subjects. Mixed-model regression will determine whether blinded treatment produces a greater normalization in mitochondrial function over the 12-week period as compared to placebo treatment over the same time period. Similar analysis will test secondary outcome measures. Assuming a medium effect size of 0.5, the study provides an 80% power assuming a 0.01 alpha (allowing correction for multiple primary end-points). Secondary outcome measures will include the Improvement item of the Clinical Global Impression Scale and behavioral scales such as the Aberrant Behavior Checklist. Multivariable logistic regression will be used to select biomarkers that can significantly predict treatment response.

Full Study Title: Effect of a Wide Spectrum Nutritional Supplement on Mitochondrial Function in Children with Autism Spectrum Disorder (ASD)

Principal Investigator: [name]; Co-Investigators: [name]

Sponsor: [name]; IND 142751; ClinicalTrials.gov ID: NCT03835117; Protocol Version 02/11/2022

Funding Source: Turnabout for Autism (Private Foundation), Pleasanton CA.

Funding	Turnabout for Autism (Private Foundation), Pleasanton CA
---------	--

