The *primary aims* of this study are to evaluate the effect of a wide-spectrum nutritional supplement on mitochondrial function in individuals with ASD. Participants entered into the trial will have abnormalities in mitochondrial function that are associated with ASD (such abnormalities are found in approximately 50% of children with ASD) but are not diagnostic of mitochondrial disease. Specifically, children with mitochondrial disease (approximately 5% of the ASD population), which is a very severe disorder, will be excluded from the study so they can pursue more intensive appropriate treatment. As we believe 50% of children with ASD have some form of atypical variations in mitochondrial function, we will target these children to improve the function of their mitochondria. We hypothesizes that a nutritional supplement designed for children with ASD will have a physiological action of normalizing mitochondrial function and cellular physiology throughout the body. To test whether the targeted nutritional supplement is superior to placebo, we will study 50 children, between the ages of 2 years 6 months and 17 years 3 months, with confirmed ASD and known abnormal variations in mitochondrial at baseline. Participants will be randomly assigned to receive active treatment or placebo for 12-weeks under double-blind conditions and at the end of the 12 weeks switch to the opposite treatment arm. Mitochondrial function will be measured at baseline and after each treatment arm in order to determine if the supplement positively influences cellular biochemistry.

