**Secondary Aim: To evaluate the effectiveness of a wide-spectrum metabolic supplement on core**

**and associated ASD symptoms.** We will determine if symptoms associated with ASD will be effected by a nutritional supplement which targets normalizing mitochondrial function. We will evaluate:

- a. Core ASD symptoms as measured by the Childhood Autism Rating Scale (CARS).
- b. Clinical Global Impression Severity and Improvement
- c. Behavior, including repetitive behavior Children Yale Brown Obsessive Compulsive Scales Modified for ASD (CYBOCS-ASD), Irritability, Social Withdrawal, and Hyperactivity subscales of the Aberrant Behavior Checklist (ABC), Parent-rated Anxiety Scale-ASD (PRAS-ASD), Caregiver Strain Questionnaire (CGSQ), Parent Targeted Problems and adaptive behavior (Vineland III).
- d. Somatic manifestations of pain, fatigue and gastrointestinal symptoms

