## 5. RESEARCH PLAN

### Trial Design

50 children with ASD and signs and symptoms of abnormal mitochondrial activity will be randomized in 1:1 ratio to receive a wide-spectrum nutritional supplement that targets mitochondrial function or placebo for 12 weeks under DBPC conditions. Each participant will serve as their own control in the cross-over design. Using a phone screen, we will identify children (age  $\geq$  2:6 and  $<$  17:3) with a diagnosis of ASD and evidence of mitochondrial function which is significantly higher or lower than average (here forth referred to as mitochondrial dysfunction). Children with suspicion of mitochondrial dysfunction will be invited to participate in a screening visit to make sure they meet including and exclusion criteria. If the screening visit is longer than 6 weeks from the prescreening, we will repeat the baseline metabolic testing to ensure an accurate baseline mitochondrial measurement. If they meet criteria, the baseline visit will be completed within 2 week but we will attempt to complete it on the same day (Table 1). Upon successful completion of the baseline visit, the participant will enter Phase 1 of the trial and will be randomized to receive active treatment or placebo for 12 weeks under DBPC conditions. At the end of the 12 weeks (end of Phase 1), the participant will return for evaluations similar to the ones conducted at baseline. Upon successful completion of the post-Phase 1 visit, the participant will start Phase 2 where they will receive active treatment or placebo, depending on what they received during Phase 1 – they will be crossed over to the opposite treatment regimen. Potential AEs, compliance and concomitant treatments will be monitored every four weeks.

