## **Statistical Analysis**

All data analysis for the primary study aims will be conducted by the principal investigator. The primary analysis will be intent-to-treat, defined as all randomized subjects. Exploratory “per protocol” analysis will be conducted on participants who adhered to protocol. Analyses will be performed with R 3.02 (<http://www.r-project.org>) or SAS 9.3 (SAS Institute, Cary, NC).

Sample Size Justification and Power Analysis: Assuming a medium effect size of 0.5, the study provides an 80% power assuming a 0.01 alpha (allowing correction for multiple primary end-points)..

Primary Hypothesis: After 12 weeks of taking the nutritional supplement will improve mitochondrial function more than taking the placebo for 12 weeks. To test this hypothesis, we will use a mixed model using baseline and all post-randomization measures of mitochondrial activity. To deal with missing post-treatment data, the model will be conditioned on all baseline values. This conditional joint response model is more tolerant of missing data than ANCOVA and is less biased than carrying baseline data forward to endpoint.

Safety analyses: Adverse events (AE) will be systematically monitored using a 34-item form. It includes specific queries about major body systems, activity level, sleep, appetite, and general health. New events, whether presumed related to treatment or not, are classified as AEs and rated as Mild, Moderate or Severe (see details below). The occurrence of an AE will be counted once at the highest level of severity (e.g., a report of mild nausea followed by a report of moderate nausea in the same child would count as an occurrence of moderate nausea). The frequency of AEs by severity will be evaluated using a Fisher’s exact test. We will pursue exploratory analyses such as survival analyses using time to AE as the response variable.

Validation of the CGI-ASD: In addition to the standard CGI-S and CGI-I we will use a new a structured CGI rating scale called the CGI-S-ASD and CGI-I-ASD respectively. We will compare the performance of the standard and new CGI rating scales. Since the CGI-ASD provide guidance for completing the ratings we will have the rater complete the standard scale before the new scale. The correspondence between each scale and other outcome measures will be studied as well as the performance of the scales as outcome measures.

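### Item 15 labels CGI-I a key primary outcome, the synopsis and Secondary Aim make it secondary, and the primary end-points behind the 0.01 alpha are never listed

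*Combined protocol and SAP*

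**What the plan says.** All of this is current text in the combined protocol and SAP.

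- **Section 5, Developmental Assessments, item 15** describes CGI-I as a measure "that will be used as a key primary outcome measure". It also defines response for a child: "Ratings of Much Improved or Very Much Improved on the CGI-I will be used to define positive response".
- **Synopsis, Statistical Methods**: "Secondary outcome measures will include the Improvement item of the Clinical Global Impression Scale". The sentences before it give the mixed model for mitochondrial function as the primary analysis and say that secondary measures will be analysed similarly.
- **Section 4, Secondary Aim, item b**: "Clinical Global Impression Severity and Improvement".
- **Section 1, Abstract**: the primary aims "of this study are to evaluate the effect of a wide-spectrum nutritional supplement on mitochondrial function in individuals with ASD".
- **Section 6, Statistical Analysis, Primary Hypothesis**: "To test this hypothesis, we will use a mixed model using baseline and all post-randomization measures of mitochondrial activity". No other primary hypothesis or model is given.
- **Section 6, Sample Size Justification** (and the Synopsis): "80% power assuming a 0.01 alpha (allowing correction for multiple primary end-points"). The end-points are neither named nor counted.
- **Section 5, Trial Design**: children are selected for "evidence of mitochondrial function which is significantly higher or lower than average". Section 4 sets normalization of that function as the aim, but no score for normalization is given.

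**The concern.** One measure has two ranks, and no passage says which prevails. A stray label would normally be harmless, because a list of primary end-points would overrule it. Here there is no such list. The power statement refers to primary end-points in the plural, which leaves room for a measure that another section calls primary.

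What is at stake is the claim that the trial may make. Suppose the mitochondrial comparison is null and CGI-I favours the supplement. Under the Synopsis, the Secondary Aim and Section 6 the primary has failed and CGI-I is a supportive finding. Under item 15 the same data could be presented as success on a primary outcome.

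The mitochondrial side has a related weakness. If some children start above average and others below, a supplement that normalizes function should lower activity in the first group and raise it in the second. A model of raw activity averages these opposite changes and can miss the effect that the trial is designed to find.

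**Working it through.** **1. The plan's own power figure.** Inputs from the documents: 50 children in a cross-over, effect size 0.5, alpha 0.01. Assumptions: a two-sided paired t-test, with 0.5 taken as the mean within-child difference divided by its SD. The noncentrality is 0.5 × √50 = 3.54 on 49 degrees of freedom, which gives power of 79.9%. The stated 80% reproduces, so the sample-size arithmetic is not at fault.

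**2. What 0.01 implies.** If 0.01 is a Bonferroni split of an overall 0.05 (neither is stated), then 0.05 / 0.01 = 5 tests. The plan names no set of five.

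**3. Rank of CGI-I, place by place.**

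| Place | Rank of CGI-I |
|---|---|
| Section 5, item 15 | key primary |
| Synopsis, Statistical Methods | secondary |
| Section 4, Secondary Aim b | secondary |
| Section 1, primary aims | not mentioned; mitochondrial function only |
| Section 6, Primary Hypothesis and model | not mentioned; mitochondrial activity only |
| Section 6, power statement | cannot be told; end-points unnamed |

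One place says primary, two say secondary, two are consistent with secondary, and the one that could settle the matter is silent.

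**4. Familywise error, illustration only.** Assumptions not in the documents: each mitochondrial measure tested at 0.01, CGI-I tested at 0.01 or 0.05, and all nulls true. For independent tests the chance of any false positive is 1 − ∏(1 − αᵢ). The last column assumes two-sided, equally correlated normal tests with correlation 0.7.

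| Tests | Independent | Correlation 0.7 |
|---|---|---|
| One measure at 0.01 | 1 − 0.99 = 1.0% | 1.0% |
| One, plus CGI-I at 0.01 | 1 − 0.99² = 2.0% | 1.8% |
| One, plus CGI-I at 0.05 | 1 − 0.99 × 0.95 = 6.0% | 5.5% |
| Five at 0.01 | 1 − 0.99⁵ = 4.9% | 3.5% |
| Five, plus CGI-I at 0.01 | 1 − 0.99⁶ = 5.9% | 3.9% |
| Five, plus CGI-I at 0.05 | 1 − 0.99⁵ × 0.95 = 9.7% | 6.9% |

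The result passes 5% only with CGI-I at 0.05 or with six near-independent tests at 0.01.

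**5. Raw activity against distance from normal.** Assume every child moves 0.5 SD toward normal and none crosses it. Let p be the fraction starting below normal. The mean raw change is 0.5p − 0.5(1 − p) = 0.5(2p − 1).

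| Split, below:above | Mean raw change | Mean reduction in distance from normal |
|---|---|---|
| 100:0 | 0.5 SD | 0.5 SD |
| 75:25 | 0.25 SD | 0.5 SD |
| 50:50 | 0 | 0.5 SD |

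The documents do not give the expected split, so these rows show a range.

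**The case against.** The strongest reply is that the primary is clear. The title, Synopsis, Abstract, Primary Aim and Primary Hypothesis all point to mitochondrial function, and the Synopsis gives CGI-I an analysis route as a secondary outcome. One phrase in a measure description disagrees. It may have been carried over from another trial, since other text does not fit this design either: a language-test review in Section 5, and a CELF-4 and an open-label extension in Section 7. The child-level responder definition does not imply primary rank; it could equally serve the planned search for predictors of treatment response.

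Most of this stands. It is why secondary is the right correction, and why a reader should not infer that the plan truly makes CGI-I co-primary. It does not remove the conflict: both ranks are in force, and the unnamed plural end-points prevent the rest of the plan from overruling item 15.

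A reader might also infer that the trial's error rate is materially inflated. The documents do not support that. They give no number of tests, no alpha for CGI-I, no correlation and no overall level, and with one mitochondrial measure plus CGI-I at 0.01 the figure is only 2.0%.

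Finally, the background section reports a single index of mitochondrial function from an earlier buccal-swab study, so one summary measure is possible here. That section does not adopt it as this trial's end-point.

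**Conclusion.** The contradiction over CGI-I is real and should be corrected before unblinding, because it affects what the trial may claim. Its size is not a percentage: the same data could be read as a failed or a met primary. The familywise figures are illustrative and do not carry the conclusion.

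The weight of the text makes CGI-I secondary. A reader might infer that it could as easily be made primary by editing the other sections. The documents do not support that. Table 1 schedules CGI-I only at weeks 12 and 24, so it has no baseline value for a model conditioned on baseline. Its response is binary, and the power statement rests on one standardized effect of 0.5. CGI-I as a primary would need its own model and power statement, and whether 50 children would suffice is unknown.

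The unnamed mitochondrial measures, and the unstated standing of the redox and biomarker items under the Primary Aim, are largely missing detail rather than contradiction. The scoring point goes further: with entry on both sides of average, raw activity does not measure normalization. The amount of cancellation depends on the split and on the assumed 0.5 SD move.

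**What to change.** Before unblinding:

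1. In Section 5, item 15, replace the words *key primary* with *secondary*, to agree with the Synopsis, the Secondary Aim and Section 6.
2. In Section 6, list by name the mitochondrial end-points tested at 0.01 and state that CGI-I is not among them. If 0.01 is a Bonferroni split of 0.05, say so and list no more than five.
3. In the primary model, use a distance-from-normal score for each listed end-point in place of raw activity, and define the normal reference value from which distance is measured.

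The cost is protocol and SAP wording plus minor analysis work. No patients, visits or procedures are added. Any primary claim on CGI-I is given up; it stays as a secondary outcome.
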